Study Centers:	Subjects will be enrolled in approximately 7 centers in Denmark, Sweden and the Netherlands.	
Study Objectives:	The aim of the study is to evaluate whether short-term, pre- emptive combination treatment with venetoclax plus acalabrutinib in patients with high risk of infection and/or CLL treatment can change the natural history of immune dysfunction in CLL in terms of the long-term risk of serious infections and diminish the need for cytotoxic chemotherapy. (Without an increased risk of infection during treatment in that group)	
	Primary Objective phase 2 part:	
	 Grade ≥3-Infection-free survival in the treatment arm compared to the observation arm 12 weeks after finishing treatment, (24 weeks after treatment initiation). This is a non-inferiority analysis as detailed in the statistical analysis plan to assure safety of the combination treatment in this preemptive trial population. 	
	Primary Objective optional phase 3 part:	
	 Grade ≥3-infection free and CLL-treatment-free survival 2 years after enrollment 	

Secondary Objective(s):

- Grade ≥3-infection free and CLL-treatment-free survival at end of treatment, 1 year and 2 years after enrollment
- Rate of overall survival (OS) and cause of death
- Treatment free survival
- Rate and CTCAE V5.0 grade of infections
- Response rate and duration according to IWCLL criteria
- Treatment related adverse events, type, frequency and severity during and for 2 years after treatment
- Immune function as assessed by immune phenotyping, functional TruCulture assays and measurements of cytokine levels

Exploratory Objective(s):

- MRD levels in bone marrow and peripheral blood
- Quality of life during and for 2 years after treatment, QLQC30 and CLL17

Study Design:

Newly diagnosed patients with CLL will be assessed by the CLL-TIM algorithm for high risk of infection and/or early CLL treatment need during the screening period. Only patients identified as at high risk, who do not currently fulfil IWCLL treatment criteria, will enter the trial. Assessment of variables for the risk profile including the baseline characteristics and laboratory result based Machine Learning algorithm CLL-TIM will be performed centrally through a plug & play model, which will be part of the eCRF system.

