- Assuming the incidence of grade ≥3 infectious events is the same in the treatment arm and the observation arm, which based on the predictive model is 10% within the first 6 months, a non-inferiority test can be performed. With a power of 80% and a sample size of 25 patients in each arm, the margin for assessment of non-inferiority will be 21%, i.e. if significantly more infections are seen in the treatment arm than in the observation arm, the treatment arm will be inferior to observation. From a clinical perspective, the margin of error is considered meaningful. The 21% margin of error is acceptable for this high-risk patient population at 24 weeks after initiating treatment/observation, particularly as clinical benefit of treatment is expected to continue for several years.
- Any pattern of AEs or individual AEs through the abovementioned DSMB assessment that indicate that the trial should be stopped.

A thorough translational immune phenotype and immune function analysis plan is adjoined to the study. Results of this translational program are included as secondary outcomes. The assessment of the grade ≥3-infection free, CLL-treatment-free survival will be qualified by the results from the translational program. Hereby, the clinical outcome from the study will be significantly strengthened by molecular and functional information about improvements in immune function.

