5.3.3 Analysis of Primary Endpoint

PRIMARY ENDPOINT, PHASE 2 PART:

Grade ≥3-Infection-free survival in the treatment arm compared to the observation arm 24 weeks after treatment/observation is initiated. The proportion of patients with the primary endpoint will be assessed at 24 weeks after enrollment using a chi-squared test of proportions. - This is a non-

inferiority analysis as detailed in statistical analysis plan to assure safety of the combination treatment in this preemptive trial population.

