In addition, an NGS capture-based assay for MRD detection based on recurrent mutations and IGHV sequence is under development. DNA is prepared from patient samples at time of MRD assessment by flow cytometry. After full enrollment, these DNA samples will be analyzed by the NGS assay to allow for direct comparison of MRD assessment by the two methods and to allow for assessment of subclonal development during and after treatment. Furthermore, BH3 profiling as

developed in collaboration with Assoc. [name], Dana Farber Cancer Institute, will be employed for assessment of sensitivity to various targeted therapies of viably frozen primary CLL cells from enrolled patients at baseline. The results of BH3 profiling will be correlated with long term outcome for the patients.

5.4 PROCESS FOR DECISION ON THE OPTIONAL EXPANSION TO PHASE 3

When the phase 2 part of the study is fully enrolled, the following assessments will form the basis for the decision on whether to expand the study to the optional phase 3 part with 212 patients in total:

- Non-inferiority for the phase 2 part as stated above should be met
- Immunophenotype analyses as outlined above have been reviewed
- Trend for benefit for patients in the treatment arm should be assessed
- DSMB do not find contraindications or safety reasons against expansion to phase 3
- Assessment by Abbvie, Acerta and the two study groups have been reviewed

The final decision to expand the study to the phase 3 part will be made by the sponsor, taking into account the input from the above-mentioned analyses and assessments.

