6. ASSESSMENT OF SAFETY

Due to the pre-emptive treatment of a patient population normally not treated, an independent DSMB assessment of infectious risk and adverse events on an ongoing basis during enrollment is included. The trial may be stopped based on the decision by the independent DSMB if increased infectious risk or AE risk is considered to outweigh the potential benefit. For these safety assessments, the treatment period (first 6 cycles of 28 days each) and the follow up period will be assessed independently to improve detection of treatment-related events vs CLL-related events. The following early stopping rules will be applied:

- Any fatal events or Grade ≥3 infectious events in the treatment arm will be reported immediately (within 7 days of notification) to the DSMB for assessment of whether the event impacts the risk-benefit of the treatment (data on similar events in the observation arm will be made available to the DSMB). All Grade ≥3 infectious events would be considered AESIs to be reported along with SAEs within 24 h in the phase 2 part.
- Assuming the incidence of grade ≥3 infectious events is the same in the treatment arm and
 the observation arm, which based on the predictive model is 10% within the first 6 months, a
 non-inferiority test can be performed. With a power of 80% and a sample size of 25 patients
 in each arm, the margin for assessment of non-inferiority will be 21%, i.e. if significantly more

infections are seen in the treatment arm than in the observation arm, the treatment arm will be inferior to observation.

- Any pattern of AEs or individual AEs through the above-mentioned DSMB assessment that indicate that the trial should be stopped.
- A thorough translational immune phenotype and immune function analysis plan is adjoined to the study. Results of this translational program are included as secondary outcomes. The assessment of the grade ≥3-infection free, CLL-treatment-free survival will be qualified by the results from the translational program. Hereby, the clinical outcome from the study will be significantly strengthened by molecular and functional information about improvements in immune function.

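### The 21-point non-inferiority margin is the excess that 25 patients per arm can exclude, so meeting it does not by itself assure safety

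*Protocol*

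**What the plan says.** The second early stopping rule in the Synopsis (Efficacy and Safety Parameters) starts from equal rates: "Assuming the incidence of grade ≥3 infectious events is the same in the treatment arm and the observation arm", a rate "which based on the predictive model is 10% within the first 6 months". It then fixes the design, "With a power of 80% and a sample size of 25 patients in each arm", and gives the margin as the result. Section 6 repeats this: "in each arm, the margin for assessment of non-inferiority will be 21" per cent.

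The Synopsis adds a judgement that section 6 does not carry. It calls the margin clinically meaningful and says: "The 21% margin of error is acceptable for this high-risk patient population at 24 weeks after initiating treatment/observation". In particular support it cites benefit expected to last several years. Neither place derives the margin from a tolerable excess of infections or writes out the treatment-arm rate that it corresponds to.

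The purpose is given in section 5.3.3 as a non-"inferiority analysis as detailed in statistical analysis plan to assure safety of the combination" treatment, and in the same sense in the Synopsis objectives and sections 2.1 and 5.3.1. The Synopsis also attaches a condition to the overall aim: "Without an increased risk of infection during treatment in that group". Section 5.4 puts this first among the conditions for expanding to 212 patients: "Non-inferiority for the phase 2 part as stated above should be met".

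**The concern.** A non-inferiority margin should be the largest excess that is clinically tolerable, and a pass should be described as excluding that excess. Here the excess is whatever 25 per arm can exclude, and a pass is described as assurance of safety. The patients have no indication for treatment and would otherwise be observed, so a real increase in serious infection is the main harm at issue.

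At stake is the conclusion drawn from a pass. As written, a treatment that raises the risk by half, or doubles it, could be reported as having met an analysis that assures safety, and would have satisfied the first condition for expansion.

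The reason given for accepting the margin also leans on later benefit. Infection-free and CLL-treatment-free survival at 2 years is the primary objective of the optional phase 3 part, so that benefit has yet to be tested.

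**Working it through.** **Inputs.** From the Synopsis and section 6: rate 10% in both arms, 25 per arm, 80% power, margin 21%. The protocol gives no significance level for this test, so one-sided 5% and 2.5% are both tried. No dropout is applied, because the protocol states no inflation for it.

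**1. Reproduce the margin.** With equal rates p and n per arm,

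margin = (z(1−α) + z(0.80)) × √(2p(1−p)/n).

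The standard error is √(2 × 0.10 × 0.90 / 25) = √0.0072 = 0.0849.

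- One-sided 5%: (1.645 + 0.842) × 0.0849 = 0.211. This matches the stated 21%. Power for exactly 21 points is 79.7%.
- One-sided 2.5%: (1.960 + 0.842) × 0.0849 = 0.238. This does not match. Power for 21 points is then 69.7%.

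So the stated figure is the excess that 25 per arm can exclude with 80% power at one-sided 5%.

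**2. State it as rates.** 10% + 21 points = 31%, a risk ratio of 31/10 = 3.1 at the boundary.

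**3. What a pass can show.** Full enumeration of two binomial counts (25 per arm, control rate 10%) gives the chance of declaring non-inferiority when the 21-point margin is properly applied. Two tests are used: the upper Wald bound below 0.21, and the Farrington–Manning score test.

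| True rate, treatment v observation | One-sided 5%: Wald / score | One-sided 2.5%: Wald / score |
|---|---|---|
| 10% v 10% | 82% / 72% | 74% / 59% |
| 15% v 10% | 57% / 47% | 47% / 34% |
| 20% v 10% | 34% / 26% | 25% / 17% |
| 25% v 10% | 17% / 13% | 11% / 7% |
| 31% v 10% | 6.2% / 4.7% | 3.7% / 2.3% |

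The last row is the error rate at the boundary and is close to nominal, so the test does its own job. The middle rows show what it leaves open.

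**4. In counts.** About 2 or 3 events are expected in the observation arm (25 × 0.10 = 2.5). At one-sided 5%, with 2 observation events a pass needs at most 3 treatment events under either test. With 3 it needs at most 4 (Wald) or 3 (score). A pass therefore needs similar observed counts, but counts this small are compatible with a wide range of true rates.

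**The case against.** The strongest reply has four parts.

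*A wide margin is normal in a small phase 2 trial, and passing at 15% v 10% is what any margin above 5 points allows.* This stands. The margin's size is a trade-off against sample size and is not an error in itself. At 80% power and 10% in both arms, a 15-point margin needs 50 per arm at one-sided 5%, and a 10-point margin 112.

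*The protocol does justify the margin and does not hide it.* This stands in part. The Synopsis calls the margin meaningful and acceptable for a high-risk population, with later benefit as added support, and the 10% and the 21% stand in the same rule. But no tolerable excess is argued, and the reader has to add the figures to reach 31%.

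*Safety does not rest on this test alone.* This stands. Every fatal or grade ≥3 infectious event in the treatment arm goes to an independent DSMB that can stop the trial. Section 5.4 also requires that the DSMB raise no safety objection, together with assessment of a trend for benefit, immunophenotype review and review by the companies and study groups. Non-inferiority is necessary for expansion but not sufficient. These safeguards are matters of judgement, however, and do not change what the primary analysis shows.

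*No finite margin can show zero increase, and the Synopsis condition concerns the treatment period, while the endpoint runs to 24 weeks.* Both are true. The first is the reason the claim should be worded as the excess excluded.

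A reader might also infer that the plan readily lets a tripled risk through. It does not: 31% is the boundary, and a true 31% passes only about 5–6% of the time at one-sided 5%.

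**Conclusion.** The point holds as one about the claim. The 21% is the absolute excess that 25 per arm can exclude (31% v 10%), and meeting it does not assure safety. At one-sided 5% a true 15% v 10% passes about 47–57% of the time and a true doubling about 26–34%. At one-sided 2.5% the figures are about 34–47% and 17–25%. These rest on the protocol's 10% control rate, no dropout, and a margin applied through a proper bound or score test. The significance level is inferred from the reproduction.

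Two stronger readings are not supported. One is that the margin is as large as the benefit phase 3 could detect. The protocol gives no phase 3 significance level, power or effect size. With 106 per arm, a 65% event risk and two-sided 5%, the detectable difference is about 19 points at 80% power but 22 at 90%, so even the direction depends on assumptions. The endpoints also differ: a 2-year composite that already counts early infections, against infection-free survival at 24 weeks. The other is that the documents imply a particular tighter margin. They do not: a 10-point margin, for instance, would again be roughly what 106 per arm can exclude (2.486 × √(2 × 0.09/106) = 0.102).

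**What to change.** Keep 50 patients and change the following.

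- **Synopsis and section 6:** state the margin as 21 percentage points absolute, 31% v 10%, and say that it is the excess 25 per arm can exclude, with the significance level that produces it. Do not rest its acceptability on long-term benefit that phase 3 has yet to test.
- **Synopsis objectives, 2.1, 5.3.1 and 5.3.3:** replace the words about assuring safety with *to exclude an absolute increase of 21 percentage points or more in grade ≥3 infection at 24 weeks*. Report the risk difference with its confidence interval, and state that a pass does not show absence of increased risk.
- **Section 5.4:** have the expansion decision consider that interval as well as the pass or fail. If the trial expands, re-estimate the 24-week risk difference in all 212 patients. Any tighter margin should be justified clinically by the sponsor.

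The cost is wording, one reported interval, and one later analysis of the 24-week data if the trial expands. No patients are added. The downside is a weaker but accurate phase 2 claim.

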1. BACKGROUND INFORMATION

1.1 CHRONIC LYMPHOCYTIC LEUKEMIA (CLL)

Chronic lymphocytic leukemia (CLL) is a malignancy of antigen reactive, mature B cells involving blood, bone marrow, and lymphoid tissues. It is the most common leukemia in Western countries with approximately 450 new patients diagnosed in Denmark each year. (lymphoma.dk)¹¹ The overall survival has significantly improved with the introduction of chemoimmunotherapy and targeted treatment, but the clinical course is very heterogeneous. ¹² Patients with CLL have an increased risk of infections. Up to 47% suffering from recurrent infections and one-third of all deaths among patients with CLL being due to infection; leading to infections being the major cause of death for treated as well as treatment naïve patients with CLL, while all other causes of death have decreased over the last decades.¹³⁻¹⁵

Figure 1-1. No improvement in infectious deaths despite improvement in overall survival over the last three decades.

da Cunha-Bang et al, Blood Cancer J, 2016

Infection 30 day mortality 10%

Treatment 1 year mortality 11%

Death

Death

[figure not shown]
Years after diagnosis

Figure 1-2. Competing risk for either infection, CLL treatment or death as first event from time of diagnosis.

Andersen et al, Haematologica, 2018

In recent work from our group, assessing the disease course for 2905 patients diagnosed with CLL, the cumulative incidence of severe infection prior to treatment was 31.6 % within 5 years of infection and 9.8 % died within one month after the infection. ¹⁶ Based on machine learning modeling, we can now identify patients with a >65% risk of infection and/or treatment within 2 years in newly diagnosed patients with CLL. (Agius et al, EHA 2018, abstract PS-1103, manuscript prepared for journal submission).

Figure 1-3. Factors with impact on risk of infection based on regular multiple regression (left) and Machine Learning (right, incomplete list, not completed).

Chemoimmunotherapy is the standard of care in first-line treatment of CLL patients without del17p or TP53 mutation; physically fit patients are treated with fludarabine, cyclophosphamide and rituximab (FCR) ¹⁷ even though recent conference proceedings have indicated that subgroups of these patients may better be treated with ibrutinib. ¹⁸ Due to the high risk of severe neutropenia and infections upon FCR treatment, bendamustine and rituximab (BR) is considered the best treatment option in patients aged >65 years. ¹⁹ However, these conventional chemoimmunotherapies are associated with side effects caused by the cytotoxic effect of chemotherapy. Therefore, there is an urgent need for alternatives, especially chemotherapy-free regimens. In the clinical setting, Danish real-world evidence demonstrates a 50% 1-year risk of severe infection after chemoimmunotherapy in CLL, with a 3-year infectious risk of 75% - thus emphasizing the impact of chemoimmunotherapy combined with the immune dysfunction of CLL.

1.2 BRUTON TYROSINE KINASE INHIBITION AND BCL-2 INHIBITION IN CLL

The B-cell receptor (BCR) pathway has recently been the core for development of new therapeutics for patients with CLL. Several molecules in the BCR pathway have been clinically targeted in CLL, with the BTK inhibitors ibrutinib and acalabrutinib and the PI3Kδ inhibitor idelalisib approved for clinical use. Acalabrutinib has shown excellent responses and an acceptable safety/toxicity profile. Similarly, the significance of the anti-apoptotic peptide bcl-2 in the pathogenesis of CLL has led to test of bcl-2 inhibitors. The bcl-2 antagonist venetoclax has proven highly effective with tumor lysis syndrome as dose limiting toxicity, 22,23 in patients with relapsed and refractory (RR) CLL. Venetoclax has been approved for CLL patients and even been shown to achieve MRD negativity.

We and others have previously demonstrated that the BTK inhibitor ibrutinib used in clinical trials of CLL can reverse immune dysfunction and improve IgA levels along with a decreased risk of infection and improvement in immune phenotype. ^{6-8,25} Translational data for patients treated with BTK inhibitors ^{6,25,26} and venetoclax ²⁷ indicate that immune function can be at least partly restored on treatment with decreasing incidence of infections over time on treatment and improved immune parameters with lowered proportion of Treg cells and decreased PD1 expression allowing for reversal of the pseudoexhausted phenotype of T cells in CLL. The combination of BTK inhibitors and venetoclax has demonstrated synergy in primary CLL cells and in several DLBCL cell lines. ²⁸⁻³⁰ Preliminary data from clinical trials combining BTK inhibitors and venetoclax did not show any new safety signals of specific importance, and no signals indicating increased risk of infection has been identified (confidential communication within the GAIA/CLL13 and VISION trials, for which the applicants are founding members). Furthermore, translational studies indicate that the protective role of microenvironmental interactions in CLL can be disrupted and impact the synergy of venetoclax in combination with BTK inhibitors. ^{31,32}

Based on former clinical trials testing early treatment at diagnosis of CLL vs treatment only at the time of symptomatic disease according to IWCLL criteria,³³ it is a dogma that only symptomatic CLL patients should be treated. However, the significant morbidity and mortality due to infections in patients with CLL prior to treatment warrants clinical trials addressing this unmet need for targeted CLL treatment that can change the natural history of CLL.

1.3 ACALABRUTINIB (ACP-196)

Acalabrutinib is an imidazopyrazine analogue with a molecular weight of 465.5 g/mol. The compound has 1 stereogenic center and acalabrutinib is the S-enantiomer. Acalabrutinib is orally bioavailable in humans and is suitable for formulating in capsules. Acalabrutinib is approved in the US for the treatment of adult patients with MCL who have received at least 1 prior therapy. It is also being evaluated for the treatment of patients with other B-cell malignancies.

1.3.1 Mechanism of Action

Acalabrutinib is a potent inhibitor of BTK in vitro and in vivo. Pharmacology models have been used to define kinase selectivity of acalabrutinib in comparison to other BTK inhibitors, and to investigate functional effects of on-target and off-target activities. Acalabrutinib shows improved selectivity for BTK compared with ibrutinib.³⁴ Functional inhibition of non-target cells (e.g., T cells, NK cells, platelets) was not observed for acalabrutinib at clinically relevant concentrations.

1.3.2 Safety Pharmacology

In vitro and in vivo safety pharmacology studies with acalabrutinib have demonstrated a favorable nonclinical safety profile; for detailed information on the safety pharmacology of acalabrutinib, refer to the Investigator Brochure.

1.3.3 Drug-drug Interaction Potential

For more detailed information on drug-drug interaction potential for acalabrutinib, refer to the Investigator Brochure.

Please refer to Concomitant Therapy section for guidance on drugs that may cause drug-drug interactions.

1.4 CLINICAL EXPERIENCE – ACALABRUTINIB

For more detailed information on the clinical experience for acalabrutinib, please refer to the Investigator Brochure.

1.4.1 Adverse Events – acalabrutinib

ADRs observed in clinical studies with 614 subjects receiving acalabrutinib monotherapy in hematological malignancies are summarized as follows (from the IB version 7.1, percentages of all grade adverse events, grade ≥3 in parentheses):

Diarrhea 40% (2.3%), Nausea 24% (1.6%), Constipation 16% (0), Vomiting 15% (1.3%), Abdominal Pain 13% (2.0%), Bruising 41% (0), Rash 22% (0.6%), Headache 42% (1.3%), Hemorrhage 12% (1.5%).

The median duration of exposure to acalabrutinib treatment across the pooled dataset was 21.9 months (range, 0 to 42.4 months). A case of a drug-induced Grade 3 tumor lysis syndrome has been reported in a CLL patient with a bulky disease in Study CL-309 (not included in the INT population).

